5.1.1.3 Criteria that Require Permanent Discontinuation of Pembrolizumab

Subjects MUST discontinue study treatment for any of the following reasons that are not related to a related adverse event:

- Withdrawal of informed consent (subject's decision to withdraw for any reason)
- Pregnancy
- Loss of ability to freely provide consent through imprisonment or involuntary incarceration for treatment of either a psychiatric or physical (e.g., infectious disease) illness.

Exceptions to Permanent Discontinuation of pembrolizumab dosing under the following situations:

- Potentially reversible inflammation (< Grade 4), attributable to a local antitumor reaction and a potential therapeutic response. This includes inflammatory reactions at sites of tumor resections or in draining lymph nodes, or at sites suspicious for, but not diagnostic of metastasis.
- Hospitalization for < Grade 2 adverse events where the primary reason for hospitalization is to expedite the clinical work-up.
- Subjects with the following conditions where in the investigator's opinion continuing study drug administration is justified:
 - Ocular toxicity that has responded to topical therapy
 - Endocrinopathies where clinical symptoms are controlled with appropriate hormone replacement therapy.

Note: Pembrolizumab may not be restarted while the subject is being treated with systemic corticosteroids except for subjects on stable doses of hormone replacement therapy such as hydrocortisone.

All subjects who discontinue treatment prematurely due to a drug-related AE or symptomatic progression prior to disease assessment at the end of treatment visit are required to return for the 3 weeks (± 1 week) after the last dose of pembrolizumab visit, unless they are switched to an alternate anti-neoplastic medication.

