6. DOSE MODIFICATIONS

Decisions to skip or modify a pembrolizumab dose will be made based on specified safety criteria as shown in the table below.

Recommended Dose Modifications of Pembrolizumab for Adverse Reactions

Treatment-Related Adverse Reaction	Severity of Adverse Reactions*	Dose Modification
Immune-Mediated Pneumonitis	Grade 2 pneumonitis	Withhold (a)
	Grade 3 or 4 pneumonitis or recurrent Grade 2 pneumonitis	Permanently discontinue.
Immune-Mediated Hepatitis	Aspartate aminotransferase (AST)/or alanine aminotransferase (ALT) more than 3 and up to 5 times the upper limit of normal or total bilirubin more than 1.5 and up to 3 times the upper limit of normal	Withhold Pembrolizumab. Resume Pembrolizumab in patients with complete or partial resolution (Grade 0 to 1) of hepatitis after corticosteroid taper.
	If no liver mets, AST or ALT more than 5 times the upper limit of normal or total bilirubin more than 3 times the upper limit of normal; if liver mets and grade 2 AST or ALT at baseline with at least 50% increase that persist for one week or more	Permanently discontinue.
Immune-Mediated Colitis		Withhold.
	Grade 2 or 3 diarrhea or colitis	Resume in patients with complete or partial resolution (Grade 0 to 1)

		of colitis or diarrhea after corticosteroid taper.
	Grade 4 diarrhea or colitis or recurrent Grade 3 diarrhea or colitis	Permanently discontinue.
Immune-Mediated Endocrinopathies (including but not limited to hypothyroidism, hyperthyroidism, adrenal insufficiency, hyperglycemia)	Grade 3 or 4	Withhold until clinically stable.
Immune-Mediated Nephritis and Renal Dysfunction	Grade 2	Withhold. Resume in patients with complete or partial resolution (Grade 0 to 1) of nephritis and renal dysfunction after corticosteroid taper.
	Grade 3 or 4	Permanently discontinue.
Other immune-mediated adverse reactions (including but not limited to myocarditis, myositis, psoriasis, arthritis, hypopituitarism, uveitis, Guillain-Barré syndrome, pancreatitis, rhabdomyolysis, myasthenia gravis, histiocytic necrotizing lymphadenitis, demyelination, vasculitis, hemolytic anemia, hypophysitis, iritis, and encephalitis) For Immune-mediated	For any of the following: Grade 2 or 3 based on severity and type Grade 3 based on severity and type or grade 4 Grade 3 or suspected Stevens-Johnson syndrome (SJS) or toxic epidermal necrolysis	Withhold (a) Permanently discontinue. Withhold

skin AEs	(TEN) Grade 4 or confirmed SJS or TEN	Permanently discontinue.

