	For any of the following: Life-threatening adverse reaction (excluding endocrinopathies) Recurrent severe immune-mediated adverse reaction Requirement for 10 mg per day or greater prednisone or equivalent for more than 12 weeks Persistent Grade 2 or 3 immune-mediate adverse reactions lasting 12 weeks or longer	Permanently discontinue.
Infusion-related reaction	Grade 1 or 2	Interrupt or slow the rate of infusion.
	Grade 3 or 4	Permanently discontinue.

*Toxicity was graded per National Cancer Institute Common Terminology Criteria for Adverse Events. Version 5.0 (NCI CTCAE V5)

(a) Resume if complete or partial resolution (Grade 0, 1) after corticosteroid taper.

Dose Limiting Toxicity (DLT) Definition:

Dose limiting toxicity is when therapy is permanently discontinued due to toxicity as defined in the dose modification table above or when the patient withdraws from treatment due to toxicity that the patient finds unacceptable.

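### Section 6 places pituitary events under two rows with different Grade 4 actions, so the same event can be a temporary hold or a permanent stop and a DLT

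*Combined protocol and SAP*

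**What the plan says.** Two rows of the Section 6 table can apply to a pituitary event.

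- **Endocrinopathies row.** Its scope is open: "Immune-Mediated Endocrinopathies (including but not limited to hypothyroidism, hyperthyroidism, adrenal insufficiency, hyperglycemia". For Grade 3 or 4 the action is "Withhold until clinically stable". The row has no permanent-stop entry and nothing for Grade 2.
- **Other-reactions row.** It names both pituitary events: "Other immune-mediated adverse reactions (including but not limited to myocarditis, myositis, psoriasis, arthritis, hypopituitarism, uveitis", and further on "hemolytic anemia, hypophysitis, iritis, and encephalitis". The entry "Grade 2 or 3 based on severity and type" is paired with withholding, with restart under footnote (a) once the event has settled to Grade 0 or 1 after a steroid taper. The entry "Grade 3 based on severity and type or grade 4" is paired with permanent discontinuation.

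Two further passages treat endocrinopathies as a class. Among the general reasons for a permanent stop, later in the same table, is "Life-threatening adverse reaction (excluding endocrinopathies" (the bracket closes there). Section 5.1.1.3 lists, among exceptions to permanent discontinuation that depend on the investigator's opinion, "Endocrinopathies where clinical symptoms are controlled with appropriate hormone replacement therapy".

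The DLT definition at the end of Section 6 has two limbs. One is permanent discontinuation for toxicity as the table defines it. The other is the patient's own withdrawal because of toxicity.

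**The concern.** Hypophysitis and hypopituitarism are disorders of an endocrine gland. A row that covers endocrinopathies without limit includes them unless something takes them out, and nothing in the table does. The other-reactions row claims them by name. At Grade 4 the two rows give different instructions, and the table does not say which prevails.

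Two things are at stake. First, two investigators who both follow the text could manage the same event differently, one holding pembrolizumab and one ending it. Second, the DLT definition takes its meaning from this table, so the same event would be a DLT for one and not for the other. Safety is the first of the two primary objectives in Section 1.1, so the classification should be reproducible.

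**Working it through.** **Inputs.** The two table rows, footnote (a), the general permanent-stop entries and the DLT definition (all Section 6); the exceptions in Section 5.1.1.3; the frequency of pituitary inflammation (Section 7.1.1); the toxicity analysis (Sections 12.3.2 and 12.4.2); the planned sample of 30 (Section 12.5). In the other-reactions row, severity entries and actions are paired in the order listed.

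**Step 1: the rows side by side for a pituitary event.**

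| Grade | Endocrinopathies row | Other-reactions row | DLT by the table |
|---|---|---|---|
| 2 | no entry | withhold | no under either row |
| 3 | withhold | withhold or permanently discontinue | no, or yes if the discontinue entry is chosen |
| 4 | withhold | permanently discontinue | no under the first row, yes under the second |

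A hold may still become permanent later under a general entry, such as a recurrent severe reaction. The table above shows the action at first occurrence. The restart conditions also differ: clinical stability in one row, return to Grade 0 or 1 after a steroid taper in the other.

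**Step 2: does another passage settle it?**

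- The general life-threatening stop leaves endocrinopathies out. That removes one route to a permanent stop at Grade 4, but it does not cancel the separate Grade 4 entry in the other-reactions row.
- The Section 5.1.1.3 exception covers only events whose symptoms are controlled on hormone replacement, and only where the investigator judges continuation justified. A Grade 4 pituitary event outside those conditions is not resolved by it.
- No sentence says that a named event is governed by the row that names it, or that the more specific class prevails.

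The Grade 4 conflict therefore remains.

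**Step 3: effect on the DLT proportion.** The protocol gives no DLT figure to reproduce, but it does give a Wilson interval, which checks the formula. With p = x/n and z = 1.96, the limits are

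[p + z²/(2n) ± z·√(p(1−p)/n + z²/(4n²))] / (1 + z²/n).

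- x = 6, n = 30: 9.5% to 37.3%, matching Section 12.5.
- x = 0, n = 30: 0%, interval 0.0% to 11.4%.
- x = 1, n = 30: 3.3%, interval 0.6% to 16.7%.

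One patient moved from one reading to the other changes the proportion by 1/30 = 3.3 percentage points.

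**Step 4: does a decision depend on it?** Section 12 plans continuous monitoring of toxicity rates and a final count. It contains no DLT endpoint, no DLT threshold and no toxicity stopping boundary. The only stopping rule, in Section 12.2, is for futility and uses tumor response.

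**The case against.** The strongest reply is that the two events are named in one row only. By ordinary drafting sense the specific entry governs, and the word *other* in that row's title suggests that it holds what the earlier rows do not. That is a plausible reading. It does not settle the matter, because the table states no such rule and the endocrinopathy exclusion from the life-threatening stop fits better with the opposite reading.

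A second reply is that a DLT on the first limb requires treatment to have actually been stopped, which is an observable act and can always be recorded. This is true. The weakness lies one step earlier: the table is what tells the investigator whether to stop.

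Three further replies stand in full, and each closes off a stronger reading that a reader might infer.

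- **Grade 3 in two entries as a contradiction across the whole row.** Both entries carry an express qualifier about severity and type, and the row spans very different conditions. That is investigator discretion and is not claimed as an error.
- **Grade 2 as a second conflict.** One row is silent and the other says to withhold. Silence is not an opposing instruction.
- **The primary safety result as a matter of choice.** Adverse events are graded by CTCAE v5.0, and a pituitary event is graded and counted the same way whichever row is read. Only the DLT label and the management change.

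**Conclusion.** The point holds in a narrow form. For a Grade 4 pituitary event the two rows give different actions, and DLT status follows whichever row is read. A Grade 3 event is affected only if the discontinue entry is chosen. The result is possible inconsistency in patient management and in DLT classification. No decision rule in Section 12 is affected.

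The size is 3.3 points per reclassified patient. This assumes that all 30 planned patients are in the denominator; each patient would weigh more if fewer were analyzed. Such events should be rare: Section 7.1.1 puts pituitary inflammation below 2% without splitting by grade, and the conflicting grades are an unstated part of that.

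Two larger figures can be derived from the documents, but neither measures this defect. At an assumed 1% to 2% per patient, the chance of at least one pituitary case among 30 is 1 − 0.99³⁰ = 26% to 1 − 0.98³⁰ = 45%. That counts any grade, the 1% is an assumption with no floor in the documents, and 2% lies just outside the stated range. Applying the 28% rate of Grade 3 or higher treatment-related events in Section 2.2 gives 0.28 × 30 = 8.4 patients. That counts every kind of event, nearly all of it irrelevant to the two pituitary entries if the Section 7.1.1 frequency is right.

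**What to change.** The sponsor's clinical team should reconcile the endocrinopathies row and the other-reactions row of Section 6 with each other, with the general life-threatening entry in the same table, and with the exceptions in Section 5.1.1.3, so that pituitary events are governed by one row. Which action applies at each grade is a clinical decision for that team, and this review takes no view on it.

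Until the text is reconciled, any Grade 3 or 4 pituitary event should be listed separately beside the DLT count, with the action actually taken, so that a reader can see the count under either reading.

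The cost is a short amendment to the wording of the table and, if needed, Section 5.1.1.3. No new data are required, because the interim listing uses adverse-event grades and treatment actions. The discretion at Grade 3 in the other-reactions row need not change for the remaining conditions.

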7. ADVERSE EVENTS AND REPORTING PROCEDURES

7.1 Potential Adverse Events

7.1.1 Pembrolizumab alone:

Pembrolizumab may cause one or more of the side effects listed below. This information is

based on data from cancer subjects in other clinical trials with pembrolizumab.

The most common side effects (greater than 5% chance of happening) of pembrolizumab are:

- Fatigue
- Skin reactions: including rash, itching, hives, redness, blisters, and dry skin. Stevens Johnson Syndrome and toxic epidermal necrolysis, are rare and potentially life threatening diseases characterized by blistering and peeling of the top layer of skin resembling that of a severe burn.
- Diarrhea
- Nausea
- Abdominal pain
- Decreased appetite
- Joint pain or stiffness
- Thyroid gland abnormalities
- Dehydration

Less common side effects of pembrolizumab (between 2-5% chance of happening) include:

- Liver function blood test abnormalities
- Dry mouth
- Vomiting
- Low electrolyte counts in your blood, for example sodium
- Lung inflammation (pneumonitis - see details below)
- Cough
- Headache
- Fever
- Muscle soreness, weakness, stiffness spasms or paralysis
- Pain in back, arms or legs
- Shortness of breath
- Constipation
- Swelling of the face, arms, or legs
- Increase in inflammatory blood proteins (e.g., lipase)
- Liver injury

Rare but potentially serious side effects (less than 2% chance of this happening but potentially serious) of pembrolizumab include:

- Low blood oxygen level
- Acute lung injury or failure
- Collection of fluid around the lungs
- Adrenal gland abnormalities
- Pituitary gland inflammation
- Changes in vision (including decreased or blurry vision), dry eye, inflammation of the eye, or bleeding into the eye
- Tingling, burning, or numbness in hands and feet
- Hepatitis
- Changes in kidney function tests and acute kidney injury or failure
- Inflammation of the mouth and lining of the digestive tract
- Inflammation of the pancreas
- Autoimmune disorders, including Guillain-Barre syndrome (associated with progressive muscle weakness or paralysis)

- Chest discomfort
- Heart palpitations
- Inflammation of the heart or its lining or blood vessels
- Chills
- Dry skin
- Diabetes
- Increased level of blood acid called ketones
- Dizziness
- Infections: including sepsis, lung infections, and skin infections.
- Hair loss
- Changes in blood pressure
- Inflammation or loss of brain nerves supplying vision and spinal cord, abnormal brain function
- Drug reaction with rash, blood cell abnormalities, enlarged lymph nodes, and internal organ involvement (including liver, kidney, and lung); known as Drug Reaction with Eosinophilia and Systemic Symptoms (DRESS)
- Myasthenia gravis, a nerve disease that may cause weakness of eye, face, breathing, and swallowing muscles. One death in a patient who received nivolumab combined with ipilimumab was considered due to myasthenia gravis and severe infection (sepsis).
- Rhabdomyolysis (muscle fiber released into the blood stream which could damage your kidney) and polymyositis (chronic muscle inflammation with muscle weakness)
- Colitis: Inflammation of intestine. It may cause abdominal pain and diarrhea with or without blood. Fever may be present. It may require you to receive additional fluids. If left untreated, this may lead to a tear in the wall of the intestine which can be serious and life threatening. Tell your study doctor right away if you have any of these symptoms.
- Guillain-Barre syndrome: A disorder characterized by progressive symmetrical paralysis and loss of reflexes, usually beginning in the legs. The paralysis characteristically involves more than one limb (most commonly the legs), is progressive, and usually proceeds from the end of an extremity toward the torso.
- Sarcoidosis: growth of tiny collections of inflammatory cells (granulomas) in different parts of your body — most commonly the lungs, lymph nodes, eyes and skin.
- Loss of color (pigment) from areas of skin
- Allergic reaction
- Rejection of organ or tissue transplant
- Graft versus host disease (GVHD): In patients who have received a transplant containing blood cells from another person (allogenic transplant), the donor's immune cells attack the normal cells. Symptoms can be rapid and severe and can occur in any organ of the body. This has resulted in death when nivolumab, an antibody similar to pembrolizumab, or nivolumab and ipilimumab were given after allogenic transplant.

Lung Inflammation (pneumonitis): It is possible that pembrolizumab may cause inflammation of the tissues of the lung. This adverse effect has been reported infrequently in patients treated with pembrolizumab. While many patients with x-ray or CT abnormalities have not developed any symptoms, some patients have developed mild to severe symptoms and in rare cases, death has occurred as a result of their lung inflammation. Signs and symptoms of lung inflammation may include difficulty breathing, pain or discomfort while breathing, chest pain, cough, shortness of breath, increased rate of breathing, fever, low blood oxygen levels, or fatigue.

Your study doctor and nurse will watch you closely for changes in your ability to breathe and

for other signs or symptoms that might show you are developing this type of lung inflammation and will perform regular tests including physical exams, measurement of oxygen levels through non-invasive testing (i.e., pulse oximeter), blood tests, chest x-rays and/or CT scans.

Please inform your study doctor or nurse AT ONCE if you experience any of the following:

- Any new or increased shortness of breath;
- Any new or increased chest pain;
- Any new or increased pain/difficulty while breathing;
- Any new or increased cough or any significant change in your type of cough; for example any new or increased mucous or blood in your cough;
- Any change in the amount of oxygen you require;
- Any fever, fatigue, or other symptoms that occur at the same time as any changes to your breathing or other lung symptoms.

If you start to develop symptoms, your study doctor will ask you to return to the clinic for additional tests, which could include a physical exam, measurement of oxygen levels, blood tests, chest x-rays, and/or CT scans. You will be monitored very closely for changes in your overall lung symptoms, monitoring may require hospitalization. You may require specific treatment in order to control pneumonitis. You may also be seen by a special doctor called a pulmonologist, who has special training to be an expert in how your lungs work.

Prolonged treatment with medicines that suppress inflammation, sometimes needed to manage the side effects of pembrolizumab treatment, may lower your body's ability to fight off certain infections (i.e., opportunistic infections). These infections may require treatment with antibiotic or antifungal medications and may be fatal.

7.1.2 Radiotherapy alone:

Radiotherapy will be delivered by standard of care palliative radiotherapy.

Radiotherapy will be administered in 3-5 treatments to 1-2 sites of disease. This will occur between the first and second dose of pembrolizumab.

Side Effects Related to Radiotherapy:

Side effects of radiation therapy are determined by the site irradiated, normal tissues in the field, and the total dose and number of treatments given. Your radiation oncologist will discuss this in detail with you and you will be asked to sign a separate consent form for the radiation therapy. In general, side effects from radiation therapy are described below.

Likely:

- Rash
- Skin irritation

Less Likely:

- Feeling tired
- Lowering of blood counts which may make infection and bleeding more likely
- Nausea

Rare, but serious:

- Development of a second cancer
- Increase in pressure in an arm or leg from inflammation that requires surgical intervention

7.2 Adverse Event Reporting

Adverse events will be graded according to CTCAE v5.0. Both Serious and Non-Serious Adverse Events will be clearly noted in source documentation and listed on study specific Case Report Forms (CRFs). The Protocol Director or designee will assess each Adverse Event (AE) to determine whether it is unexpected according to the Informed Consent, Protocol Document, or Investigator’s Brochure, and related to the investigation. All Serious Adverse Events (SAEs) will be tracked until resolution or until 60 days after the last dose of the study treatment. Immune related serious adverse events (irSAEs) definitely related to study treatment will be captured for 6 months after the last dose of study treatment.

SAEs CTCAE Grade 3 and above, and all subsequent follow-up reports will be reported to the Stanford Cancer Institute Data and Safety Monitoring Committee (DSMC) using the study specific CRF regardless of the event’s relatedness to the investigation. Following review by the DSMC, events meeting the IRB definition of ‘Unanticipated Problem’ will be reported to the IRB using eProtocol within 10 working days of DSMC review, or within 5 working days for deaths or life-threatening experiences.

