1. OBJECTIVES

1.1. Primary Objective

The primary objectives of this study are to assess 1) the safety and 2) efficacy of combining Anti-PD-1/PD-L1 blockade with palliative radiation therapy in patients with Stage IV Merkel Cell Carcinoma. Efficacy for the primary objective will be tumor response rates (CR, PR, SD, irCR, irPR, irSD) at both irradiated and unirradiated sites.

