- Vital sign measurements will include weight, temperature, pulse, and resting systolic and diastolic blood pressure. Vital sign measurements of pulse, and systolic and diastolic blood pressure will be collected prior to the infusion of anti-PD-1/PD-L1.
- Physical examination
- ECOG Performance Status
- Clinical laboratory tests (as outlined in the screening phase) (taken and results reviewed prior to study drug administration):
 - Hematology
 - Serum chemistry
 - TSH w/Reflex FT4- week 13 only (for patients who continue pembrolizumab past week 10)
- Blood (optional) for investigational immune response assays at 2 weeks (± 1 weeks) and 8 weeks (± 1 weeks) after completion of radiation therapy.
- Concomitant medications
- Adverse event assessment
- Optional Tumor biopsy

Follow-up

Patients will be seen for an end of treatment visit 3 weeks (± 1 week) after the last pembrolizumab dose and again for follow up visits every 3 months (± 1 month) for 2 years and then every 6 months (± 1 month) for years 3-4 and again at year 5 (± 1 month) per SOC thereafter until progression of disease by imaging criteria or increased symptomatology that requires another therapy. Follow up visits will be performed until 5 years from the last dose of pembrolizumab and will then become optional and SOC.

The following procedures will be performed at each scheduled follow-up visit ± 1 month during the first 2 years. During years 3-5 the clinical laboratory tests will be performed only once per year.

- Measurements of vital signs (resting systolic and diastolic blood pressure, pulse, respiratory rate, and temperature) and weight
- Physical examination
- ECOG Performance Status
- Clinical laboratory tests
 - Hematology
 - Serum chemistry
 - TSH w/Reflex FT4

- Concomitant medications (for the first 2 years)
- Adverse event assessment (for the first 2 years)
- Status of new and continuing AEs and SAEs (at minimum, collected up to 60 days following last dose of pembrolizumab, 6 months for irSAEs definitely related)
- Relevant imaging studies for tumor measurements
- Optional Tumor biopsy

Survival Follow-Up Assessment for all Subjects

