After a subject progresses or changes therapy due to symptomatology, they will enter survival follow-up. In the event a subject withdraws from the treatment phase of the study or discontinues from all other study procedures, the investigators may continue to contact the subject (with his/her agreement) for the collection of survival follow-up data. The subject's decision should be documented in the source records. If possible, contact will be made for all subjects enrolled in the study, regardless of enrollment date. If possible subjects or their caregivers will be contacted every 6 months (± 2 weeks) for 5 years from the last dose of pembrolizumab and inquiries will be made about survival data and/or death date.

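### After 60 days from the last dose, patients who have left follow-up visits are assured capture of immune-related SAEs only when judged definitely related, so late toxicity can be under-counted and its capture depends on progression status

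*Combined protocol and SAP*

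**What the plan says.** Section 1.1 puts safety first: "The primary objectives of this study are to assess 1) the safety and 2) efficacy".

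Section 7.2 sets two windows after treatment. For SAEs in general: "All Serious Adverse Events (SAEs) will be tracked until resolution or until 60 days after the last dose of the study treatment". For late immune-related SAEs (irSAEs), those "definitely related to study treatment will be captured for 6 months after the last dose". The Follow-up part of section 4 gives the same pair as a floor, "at minimum, collected up to 60 days following last dose of pembrolizumab, 6 months for irSAEs definitely related", and footnote g of the study calendar (section 9) restates the 6-month irSAE rule.

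The procedures at follow-up visits also include a wider item with no relatedness condition: "Adverse event assessment (for the first 2 years". Those visits run only "until progression of disease by imaging criteria or increased symptomatology that requires another therapy". Then: "After a subject progresses or changes therapy due to symptomatology, they will enter survival follow-up". Survival follow-up is a six-monthly enquiry about survival, and the calendar marks no adverse event evaluation in the post-study column.

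Sections 12.3.2 and 12.4.2 plan continuous monitoring of toxicity rates and a count at the end. They name no common window and no adjustment for length of follow-up.

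**The concern.** Two features combine. First, between 60 days and 6 months after the last dose, the only irSAEs the plan guarantees to record are those whose cause is judged certain. The protocol defines no causality scale, and certainty is hard to reach when two treatments are combined and a further therapy may have started. Second, the wider, unfiltered assessment is available only while a patient remains in follow-up visits, and a patient leaves these because of the efficacy outcome.

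A simple count then adds up patients who were observed for different lengths of time and under different rules, with the difference tied to progression. Any loss of late events can only lower the count. In a trial of 30 patients, one or two unrecorded serious events could change how the safety of the combination is read.

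**Working it through.** **The plan's own figure.** The only design figure is in section 12.5 and concerns response. The Wilson 95% interval for 6/30 is 9.5% to 37.3%, as stated. The probability of a half-width of at most 15.5% at n = 30 and a true rate of 20% is P(X ≤ 8) = 0.871, which agrees with the stated 87%. Nothing is sized on safety, so there is no stated safety figure to reproduce.

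**What is assured after the last dose.**

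| Patient | AEs and SAEs | irSAEs, 60 days to 6 months | After 6 months |
|---|---|---|---|
| Stops treatment progression-free (CR, PR or SD) and stays so | Assessed at visits, up to 2 years | All, through visits | All, through visits, to 2 years |
| Stops because of progression | 60 days minimum | Definitely related only | Nothing assured |
| Progresses later, during follow-up visits | At visits until progression | All until progression, then definitely related only | At visits until progression |

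For a patient who stops because of progression, the last adverse event evaluation in the calendar is the end of treatment visit, 3 weeks (± 1 week) after the last dose. The 60-day contact in footnote g is written for subjects who withdraw and do not return. So even the 60-day minimum has no scheduled collection point for such a patient.

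**Illustration.** The documents give no late irSAE rate and no share judged definite. Assume:
- a constant hazard λ of a first irSAE after the last dose, 0.5% to 2% per month;
- a share q judged definitely related of 25%, 50% or 75%;
- nothing recorded beyond the minimum.

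Let F(d) = 1 − exp(−λd/30.44), with d in days.

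At λ = 1% per month: F(60) = 1.95%, F(183) = 5.84%, F(730) = 21.3%.

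- Captured by 6 months under the minimum windows = F(60) + q[F(183) − F(60)]: 2.9%, 3.9% and 4.9% for q = 25%, 50% and 75%.
- Share missed = (1 − q)[F(183) − F(60)]/F(183). For q = 25%: 0.75 × 3.88/5.84 = 50%. For q = 50%: 33%. For q = 75%: 17%.
- Over λ from 0.5% to 2%, these shares move by about one percentage point or less.

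**Effect on a comparison by progression status.** With the same true hazard, a patient assessed for the full 2 years would show 21.3% against 2.9% to 4.9%. Over the whole range of λ and q the apparent ratio is about 4.0 to 7.7, produced by unequal collection alone. This sets the longest window against the shortest.

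**Upper bound in patients.** Suppose all 30 had only the minimum windows and 10% (assumed) had an irSAE between 60 days and 6 months. Expected events: 30 × 0.10 = 3.0. Recorded: 3.0 × q = 0.75, 1.5 and 2.25. Chance of recording none: (1 − 0.10q)^30 = 47%, 21% and 10%, against 0.90^30 = 4% without the filter.

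**The case against.** The strongest reply is that the windows are floors. Section 4 and footnote g both word the 60 days as a minimum, and no text orders later or less certain events to be discarded. Section 7.2 also sends SAEs of Grade 3 and above to the DSMC whatever their relatedness, and section 4.2 asks all who discontinue to comply with section 4 follow-up. This stands, and it limits the claim to what the plan assures. But a floor still leaves capture beyond it to chance. The DSMC sentence sets no time window, and section 4 itself moves progressing patients to survival follow-up.

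A reader might infer more than the text supports:

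- **That the windows are 2 years in responders and 60 days in patients who progress.** The long window belongs to everyone who is progression-free, including stable disease. A patient who progresses during follow-up visits is assessed until then. Because treatment continues to progression, a responder who stops for progression has the same minimum as an early progressor. The 12-fold contrast (730/60 = 12.2) is the extreme case only.
- **That about 10 of 30 patients are affected.** This takes 100 − 56 − 10 = 34% from the pembrolizumab study in section 2.2, and 0.34 × 30 = 10.2. Those patients were treatment-naive. This trial also admits pretreated patients, and section 12.2 expects 20% response. Best response does not say who later leaves follow-up visits. Even on that figure, with 10% assumed to have a late event, about one event is at stake.
- **That half to three quarters of late events would be lost.** That is one minus an assumed definite share of 25% to 50%, and it leaves out the first 60 days.
- **That a primary safety endpoint is biased.** None is defined: the primary endpoint in section 12.3 is the complete response rate. Dose-limiting toxicity (section 6) is permanent discontinuation or withdrawal for toxicity, which post-treatment windows hardly touch.

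It can also be argued that a strict causality filter is reasonable once another therapy has begun. A causality field serves that purpose without losing the event.

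**Conclusion.** The concern holds in a limited form. As written, the plan assures late irSAE capture only for definitely related events once a patient has left follow-up visits, and leaving depends on progression. With an unadjusted count as the only analysis, late irSAEs can be under-counted, and rates by outcome would not be comparable.

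The size cannot be derived from the documents. The 50% to 17% missed within 6 months of the last dose applies to patients with only the minimum windows. It rests on an assumed definite share of 25% to 75%, a constant hazard, and no recording beyond the minimum. The absolute number is probably small, perhaps one or two events in 30 patients, and on-treatment safety is largely intact.

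The documents also disagree on who enters survival follow-up. Section 2.4 includes patients who stop for unacceptable toxicity. Section 4 names only progression or change of therapy, and section 4.2 keeps all who discontinue under section 4 follow-up. On the first reading, toxicity itself could shorten the window.

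This is worth correcting because it concerns a primary objective and costs little.

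**What to change.** 1. **Collection (section 4 Follow-up, section 7.2, section 9 footnote g).** Replace the definitely-related condition. Record all irSAEs up to 6 months after the last dose in every treated patient, whatever the progression status, with causality as a separate field. If a filter is kept, set it at possibly related or higher and define the scale. Use the six-monthly contact or record review that already exists.
2. **Analysis (sections 12.3.2 and 12.4.2).** Report toxicity over a window common to all patients and measured from the first dose, or as a rate per person-time of adverse event follow-up. A window that ends a set time after the last dose would not do, because treatment runs to progression and the window would still lengthen with benefit. List later events in patients still in follow-up separately.
3. **Consistency.** Reconcile section 2.4, section 4 (Follow-up and Survival Follow-Up), section 4.2, section 7.2 and the calendar with footnote g on who enters survival follow-up and what adverse event collection applies there.

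The cost is a few more questions at an existing contact, slightly more SAE data entry, and some events of uncertain cause after subsequent therapy, which the causality field handles. Because that contact is made only where possible, some gaps will remain and should be reported. Sample size and patient management do not change.
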